3.4. Exploratory Variables

The following endpoints will be used to evaluate the time to onset of clinical response to EDP1815:

- Time to first achievement of EASI-50
- Time to first achievement of sustained* EASI-50
- Time to first achievement of IGA of 0 or 1 with a 2-point improvement from baseline
- Time to first achievement of a ≥ 2 point in improvement in PP-NRS score, in participants with a score of ≥ 2 at baseline
- Time in days to first sustained** ≥ 2 point in improvement in PP-NRS score, in participants with a score of ≥ 2 at baseline
- Time to first achievement of a ≥ 4 point in improvement in PP-NRS score, in participants with a score of ≥ 4 at baseline
- Time in days to first sustained** ≥ 4 point in improvement in PP-NRS score, in participants with a score of ≥ 4 at baseline
- Time to first achievement of a ≥ 2 point in improvement in SD-NRS score, in participants with a score of ≥ 2 at baseline
- Time in days to first sustained** ≥ 2 point in improvement in SD-NRS score, in participants with a score of ≥ 2 at baseline

* Sustained EASI-50 response is defined as one which is present on at least two consecutive visits.

** Sustained PP-NRS or SD-NRS response is one which is present at all days where the diary is completed in a minimum of a 14-day period

The following endpoints will be used to evaluate other aspects of the efficacy of EDP1815 as a treatment for atopic dermatitis at Weeks 4, 12 and 16 unless otherwise specified:

- Percentage of Participants Achieving Investigator's Global Assessment (vIGA) of 0 or 1 with a ≥ 2 Point Improvement from screening
- Mean absolute change and percentage change from Screening in EASI Score
- Percentage of Participants developing skin infections requiring topical or systemic antibiotic treatment [Time Frame: Week 16]
- Changes from baseline in SF-12 MCS and PCS scores
- Changes from baseline in HADS anxiety and depression scores
- Changes from baseline in ADCT scores
- Daily changes from baseline in the PP-NRS and SD-NRS [Timescale: Days 2 to 140]

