5.1. Inclusion criteria

To be eligible to participate in this study, all of the following criteria must be met:

1. Must have given written informed consent (signed and dated) and any authorizations required by local law and be able to comply with all study requirements.
2. Males or females aged ≥ 18 and ≤ 75 years old at the time of informed consent.
3. A diagnosis of atopic dermatitis (AD) meeting Hanifin and Rajka criteria for AD at screening ([Appendix 14.1](#)) with patient- or clinician- reported disease duration of at least 6 months.
4. Have severity of atopic dermatitis meeting the below criteria at both Screening and Day 1:
 - i. An IGA of 2, 3 or 4 on the vIGA scale, and;
 - ii. A BSA of $\geq 5\%$, and;
 - iii. An EASI score of ≥ 6 .

A cap will be set for each of the three IGA severity grades. When this cap is reached, Sponsor will notify sites that participants with severity score at Screening and/or Day 1 matching the closed stratum should be considered ineligible according to Inclusion Criterion 4i.

5. All participants must agree to use a bland additive-free, sodium lauryl sulfate (SLS)-free, and fragrance-free emollient cream, gel or ointment twice daily (or more, as needed) for at least 14 consecutive days immediately prior to randomization and must continue this treatment twice daily throughout the trial. See [Section 6.9.1.1. Background Therapy](#).
6. Meet the following contraception criteria:
 - i. Male participants:
 - i. A male participant must agree to use contraception as detailed in [Appendix 14.3](#) of this protocol during their participation in this study and for a period of 90 days after the last dose and refrain from donating sperm during this period.
 - ii. Female participants:
 - i. A female participant is eligible to participate if she is not pregnant, not breastfeeding, and at least 1 of the following conditions applies:
 1. Not a WOCBP as defined in [Appendix 14.3](#) or
 2. A WOCBP who agrees to follow the contraceptive guidance in [Appendix 14.3](#) during their participation in this study, 28 days prior to the first dose and for at least 1 complete menstrual cycle (≥ 30 days) after the last dose.

Agrees to not increase their usual sun exposure significantly during the study.

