11.4.1. Analysis of Primary Estimand

The primary estimand will be analyzed using a logistic regression with parameters for treatment group, baseline IGA score and baseline EASI score.

Body mass index, gender, race, and region will also be considered and included in the model if found to be significant.

The actual and predicted probability of EASI-50 response in each treatment group together with the estimated odds ratios and associated confidence intervals for each treatment difference will be displayed together with p-values for the comparisons of active treatment vs pooled placebo.

Actual and predicted probabilities of EASI-50 at Week 16 for each treatment group will be plotted.

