11.8. Determination of Sample Size

Cohorts 1-3

The sample size was calculated using the assumption that data from the placebo participants in the three cohorts can be pooled prior to comparison with the EDP1815 treatment groups. No adjustments for multiple testing have been made.

The primary efficacy endpoint is the achievement of EASI-50 at Week 16. The pooled placebo response rate is estimated to be approximately 25% and a doubling of this to 50% for EDP1815 would be considered as clinically meaningful.

Using a two-sided test at the 5% level of significance, 58 participants in each treatment group would give 80% power to detect a difference in one of the EDP1815 cohorts compared to the pooled placebo group. There would also be more than 90% power to compare the pooled EDP1815 6.4×10^{11} daily dose or all the EDP1815 group to the pooled placebo group.

Under the assumption of a 20% drop-out of participants prior to Week 16 this will require a total of at least 73 participants to be enrolled in each treatment group. In order to allow for the 3:1 randomization in each cohort this has been adjusted to 75 participants per treatment group to give a total of 300 participants recruited. With 75 EDP1815 participants and 25 placebo participants in each of the three cohorts.

Cohort 4

Using the same assumptions relating to the placebo rate, clinically meaningful difference, significance level, and drop-out rate as above for Cohorts 1-3, approximately 70 participants are required in each of the EDP1815 8.0×10^{10} and Cohort 4 Matched Placebo groups to provide approximately 80% power in detecting a difference between EDP1815 and placebo in Cohort 4.

In order to allow 50% of the placebo control group to be concurrent controls and 50% to be historic matched controls from Cohorts 1-3, a 2:1 randomization will be used to enroll 70 EDP1815 8.0×10^{10} subjects and 35 placebo participants to Cohort 4.

If sensitivity analyses indicate that pooling of the Cohort 4 placebo group with the Cohort 1-3 matched placebo data is inappropriate, then the power of the comparison between the Cohort 4

EDP1815 and placebo groups is approximately 65% if only Cohort 4 placebo participants could be used in the treatment comparisons.

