9.3.3 Main Analytical Approach

The primary analysis will be performed using a logistic regression model. The model will include parameters for treatment group, baseline vIGA score and baseline EASI score. As described in [Section 9.2](#) additional covariates for baseline factors will be assessed using this model for inclusion in all efficacy models. Only Week 16 data will be included in the model.

Treatment will consist of 4 levels (all placebo, cohort 1 EDP1815, cohort 2 EDP1815, cohort 3 EDP1815). Baseline vIGA will consist of 3 levels (2, 3 and 4).

The following treatment differences will be estimated:

- Cohort 1 EDP1815 vs Pooled placebo
- Cohort 2 EDP1815 vs Pooled placebo
- Cohort 3 EDP1815 vs Pooled placebo
- Cohorts 2+3 EDP1815 vs Pooled placebo*
- All EDP1815 vs Pooled placebo*
- Cohort 2 EDP1815 vs Cohort 3 EDP1815**
- Cohort 1 EDP1815 vs Cohort 2 EDP1815**

* Comparisons between pooled EDP1815 groups and pooled placebo will be considered as secondary analysis.

** Comparisons between EDP1815 treatment groups will be considered as exploratory analysis.

The comparisons between pooled EDP1815 groups* and comparisons between EDP1815 treatment groups** will be done using contrasts (LSMESTIMATE statement) within the relevant SAS procedures.

The actual and predicted probability of EASI-50 response at Week 16 in each treatment group together with the estimated odds ratios and associated confidence intervals for each treatment difference will be displayed. P-values will be displayed for the comparisons of active treatment (individual and pooled) vs pooled placebo.

Vertical bar plots for the actual and predicted probabilities of EASI-50 at Week 16 for each treatment group will be plotted.

The primary analysis approach will be repeated using the 4 supplementary estimands described in [Section 9.3.2](#).

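### The EASI models adjust only for the Day 1 score; adding the Screening EASI already collected would be a small efficiency gain (about 0 to 2 power points), and leaving it out is not an error

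*Protocol*

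**What the plan says.** Protocol 5.1 (criterion 4) asks participants to "Have severity of atopic dermatitis meeting the below criteria at both Screening and Day 1", including an EASI of at least 6. Baseline is the last value before the first dose (protocol 11.2, SAP 5.3.1.2), which is normally Day 1.

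Protocol 11.4.1 states: "The primary estimand will be analyzed using a logistic regression with parameters for treatment group, baseline IGA score and baseline EASI score". SAP 9.3.3 agrees: "The model will include parameters for treatment group, baseline vIGA score and baseline EASI score". Only BMI, sex, race and region may be added, by forward selection at p<0.05 (SAP 7.2 and 9.2). The EASI MMRM and GLMM use the same single baseline score (SAP 9.4.1.2 and 9.4.2.2).

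Screening EASI enters efficacy only through an endpoint in protocol 3.4 and SAP 9.5.1.1: "Mean absolute change and percentage change from Screening in EASI Score". Protocol 11.4.5 says that exploratory endpoints are summarised without inference.

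**The concern.** EASI-50 compares Week 16 with one Day 1 measurement, in a disease that protocol 1.1 describes as variable and prone to flares. Two people with the same Day 1 score can have different usual levels of disease. A second pre-dose score says something about that level, and so about the chance of halving the Day 1 score whatever the treatment. If this variation can be explained but is left in the model, the odds ratios are tested with slightly less power than the collected data allow. What is at stake is precision only: Day 1 fluctuation falls on all randomised arms alike.

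**Working it through.** **1. The plan's own figure.** Protocol 11.8 gives the rates ("The pooled placebo response rate is estimated to be approximately 25% and a doubling of this to 50% for EDP1815") and the result ("Using a two-sided test at the 5% level of significance, 58 participants in each treatment group would give 80% power to detect a difference"). With a pooled rate of 0.375:

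n = [1.960·√(2·0.375·0.625) + 0.842·√(0.25·0.75 + 0.50·0.50)]² / 0.25² = 57.7, so 58 per group.

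Power at 58 per group is 80.2%. With 20% drop-out, 58/0.8 = 72.5, so 73. The plan's figures reproduce.

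**2. What the covariate must explain.** As an approximation, power = Φ[(1.960 + 0.842)/√(1 − R²) − 1.960], where R² is the partial R² of Screening EASI given treatment, Day 1 EASI and vIGA. R² = 2.5% gives 81.0% and R² = 5% gives 82.0%. A gain of 1 to 2 points therefore needs a partial R² of about 2.5% to 5%. The documents give no EASI SD, no Screening-to-Day 1 correlation and no partial R².

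**3. What the gain depends on.** Assume a log-EASI SD of 0.6 (variance 0.36), of which a share ICC persists between visits, and a true individual change with SD c. Ignoring the entry threshold and vIGA, the variance of the usual level given Day 1 is 0.36·ICC·(1 − ICC). A second score of equal quality divides it by (1 + ICC). At ICC 0.8 it falls from 0.0576 to 0.0320. The variance of the log change given Day 1 is 0.0576 + 0.36·0.2 + c², so the partial R² on the continuous scale is:

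- c = 0.3: 0.0256/0.2196 = 11.7%
- c = 0.5: 0.0256/0.3796 = 6.7%
- c = 0.8: 0.0256/0.7696 = 3.3%

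The more individual courses differ after baseline, the less Screening can add. Cutting the change at 50% loses part of these values, so the binary endpoint needs simulation.

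**4. Simulation of the planned model.** Four treatment levels, 58 per group, three-level vIGA, Day 1 EASI, two-sided Wald test at 5%, EASI at least 6 at both visits, rates set to 25% and 50%. There were 3,000 trials with three comparisons each, so each gain carries about 0.3 to 0.4 points of Monte Carlo error. Power is shown for EASI entered untransformed. Gains were taken before rounding.

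| ICC | c | Power without | Power with | Gain | Gain, log EASI |
|---|---|---|---|---|---|
| 0.6 | 0.3 | 83.1% | 84.6% | +1.4 | +1.9 |
| 0.6 | 0.5 | 82.1% | 83.3% | +1.2 | +1.1 |
| 0.6 | 0.8 | 81.3% | 81.8% | +0.6 | +0.7 |
| 0.8 | 0.3 | 80.7% | 82.8% | +2.1 | +2.4 |
| 0.8 | 0.5 | 80.8% | 82.0% | +1.2 | +1.6 |
| 0.8 | 0.8 | 80.2% | 80.8% | +0.5 | +0.7 |
| 0.9 | 0.3 | 79.8% | 81.7% | +1.9 | +2.1 |
| 0.9 | 0.5 | 80.0% | 80.8% | +0.9 | +1.0 |
| 0.9 | 0.8 | 80.7% | 81.2% | +0.5 | +0.6 |

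The untransformed gains average a little over 1 point. At ICC 0.8 and c = 1.0 the gain is +0.4 (log EASI +0.8). Type I error is 5.2% with and without the covariate.

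**5. Features that shrink the gain.** Under the primary estimand, recent rescue use and related withdrawal, among other events, count as non-response. With 15% random composite non-responders (an assumed rate), the untransformed gains at c = 0.3, 0.5 and 0.8 are +1.7, +1.2 and +0.7 (ICC 0.8) and +1.6, +0.4 and +0.1 (ICC 0.9). The highest gain with log EASI is +2.0. Adding noise to the Screening score alone gives +0.8 to +1.5.

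Two further simulations of the four-group model gave less. One, at 60 per arm, found 0.9 to 1.1 points, falling to 0.1 to 0.8 with 15% composite non-response and Screening-only variation of log SD 0.3 to 0.5. The other found 0.5 to 1.5 points, falling to about 0 to 0.6 with composite non-response, a noisier Screening score, or both. A plain two-group fit (58 against 58) gives about 0 to 1.6, mostly below 1.

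**The case against.** The strongest reply is that nothing here is wrong. Baseline is clearly defined, the model already adjusts for baseline EASI and vIGA, randomisation is stratified by Day 1 vIGA, and using one baseline score is common. That stands: this is an option for efficiency, not a defect.

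A reader might infer that Screening EASI shows whether a Day 1 score was transiently high. The documents do not support that. Emollient instructions are issued at the end of the Screening visit (protocol 7.1), and twice-daily emollient is required for at least 14 days before randomisation (5.1). Topical agents need only stop 14 days before randomisation (5.2, criterion 7), and Screening may be up to 28 days before Day 1. A higher Day 1 score may reflect washout, and a lower one emollient benefit. Screening EASI is a second severity measure taken under possibly different conditions. It remains a valid covariate because it precedes randomisation, and the fitted coefficient takes whatever predictive value it has.

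A reader might also infer that the covariate costs nothing and is never missing. It needs no new data, but it adds a parameter correlated with Day 1 EASI. It also shifts the conditional odds ratio slightly (median log odds ratio about 1.15 to 1.19 in one mid-range simulation). The full analysis set is everyone randomised (protocol 11.1.1), and the SAP plans a listing of participants who did not meet entry criteria, so complete data are likely but not guaranteed. If the Day 1 score is missing, the Screening score becomes the baseline and the two covariates coincide.

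**Conclusion.** The point holds as a minor efficiency improvement. The EASI models leave out a pre-randomisation score that every eligible participant has, and adding it would not harm type I error. The supportable size is roughly 0 to 2 power points per comparison, about 1 under mid-range assumptions. The upper end needs true individual change to vary little (log SD about 0.3 to 0.5). With log SD 0.8 to 1.0, the gain is about 0.1 to 0.9. A flat claim of 1 to 2 points would go too far, because the log-EASI SD, the ICC, the SD of change and the composite non-response rate are all assumed. Nothing here suggests that the planned primary analysis is biased or underpowered.

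**What to change.** In SAP 9.3.3 and protocol 11.4.1, add Screening EASI as a fixed, pre-specified covariate beside Day 1 EASI and vIGA, outside the stepwise selection of SAP 9.2. Carry it into the supplementary estimands, the EASI GLMM and MMRM, and the Cohort 4 models. SAP Addendum 4.2 carries over only covariates that were selected, so a fixed term should be named there. Keep EASI-50 defined from Day 1.

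State a rule for a missing Screening score, and for a missing Day 1 score, where the two covariates are the same value. Note that the odds ratio is then conditional on both scores.

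Settle this before Cohorts 1-3 are unblinded, since they are locked and analysed ahead of Cohort 4 (protocol 11.7) and their efficacy results are then final (SAP 7.4.1). After that point, use the covariate for those cohorts only in a labelled sensitivity analysis.

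The cost is one parameter per model and short edits to the sections named, with no new visits, data or participants.

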4. STUDY DESIGN

4.1. Study Description

This is a randomized, double-blind, placebo-controlled study to evaluate the efficacy, safety and tolerability of EDP1815 as compared to placebo in participants with mild, moderate and severe atopic dermatitis.

This study will consist of 4 cohorts with a possible interim analysis prior to end of recruitment in Cohorts 1, 2 & 3. The purpose of this interim analysis is to check the assumptions around placebo response rate.

Approximately 100 participants will be randomly allocated to each of Cohorts 1, 2, & 3. These cohorts will run concurrently. Within each cohort, participants will then be randomized to treatment in a 3:1 ratio (75 to EDP1815, 25 to placebo). Therefore, across Cohorts 1, 2, & 3, approximately 225 participants will be randomly assigned to receive EDP1815, and 75 participants will be randomized to matching placebo for 16 weeks. Following end-of-treatment assessments, participants may enter a 4-week post-treatment follow-up period or may elect to participate in an Open Label Extension (OLE) protocol for EDP1815, if available.

- **Cohort 1:** 1.6×10^{11} total cells of EDP1815 or matching placebo administered as 2 capsules once daily.
- **Cohort 2:** 6.4×10^{11} total cells of EDP1815 or matching placebo administered as 2 capsules once daily.
- **Cohort 3:** 6.4×10^{11} total cells of EDP1815 or matching placebo administered as 1 capsule of 3.2×10^{11} cells twice daily.

Cohort 4 will run after enrollment is completed in Cohorts 1, 2, & 3. Approximately 105 participants in this cohort will be randomized to treatment in a 2:1 ratio (70 to EDP1815, 35 to placebo). Participants will be treated for 16 weeks. Following end-of-treatment assessments, participants may enter a 4-week post-treatment follow-up period or may elect to participate in an Open Label Extension (OLE) protocol for EDP1815, if available.

- **Cohort 4:** 8.0×10^{10} total cells of EDP1815 or matching placebo administered as 1 capsule once daily.

4.2. Study Duration per Participant

All cohorts will consist of:

- Up to a 4-week Screening Period
- A 16-week Treatment Period
- A 4-week Post-Treatment Follow-up Period

Total participant duration is up a maximum of 24 weeks from screening to safety follow-up, unless they elect to participate in the OLE protocol, and their maximum participation in this study would be 20 weeks.

The end of the study is defined as the date of the last visit of the last participant (LPLV).

4.3. Planned Number of Participants

This study will be conducted as a multi-center study at approximately 60 centers globally. Approximately 405 total participants will be randomized and treated with EDP1815 or matching placebo.

4.4. Anticipated Regions and Countries

This study may be conducted as a multi-regional study at centers located in North America, Europe and Asia Pacific.

4.5. Schedule of Study Assessments

Table 4-1: Schedule of Assessments

Procedure	Screening	Treatment Period							Week 20 Visit	Early Termination Visit ^a	ET Follow- Up Phone Call ^a	Rescue Therapy Unscheduled Visit ^b
		1	15	29	57	85	113	141				
Day	-28 to -1	1	15	29	57	85	113	141				
Week	-4 to -1	0	2	4	8	12	16	20				
Visit window (days)	--	--	+/-3	+/-3	+/-3	+/-3	+/-3	+3		+ 3		
Informed consent ^c	X											
Inclusion and exclusion criteria	X	X ^d										
Demography	X											
Medical history and current medical conditions (including smoking status) ^e	X											
Full physical examination ^f	X	X					X		X			
Brief physical examination ^f			X	X	X	X		X				
Height ^g	X											
Weight ^g	X	X		X			X	X	X			
Pregnancy test ^h	X	X		X	X	X	X	X	X			
12-lead ECG ⁱ	X			X			X	X	X			
Laboratory assessments (hematology including eosinophils, biochemistry, urinalysis)	X	X ^d	X	X	X	X	X	X	X			
OPTIONAL Biomarker (blood) collection: DNA Collection		X										
Biomarker (blood) collection: Inflammation immune surveillance in circulation		X	X				X	X	X			

Procedure	Screening	Treatment Period							Week 20 Visit	Early Termination Visit ^a	ET Follow- Up Phone Call ^a	Rescue Therapy Unscheduled Visit ^b
		1	15	29	57	85	113	141				
Day	-28 to -1	1	15	29	57	85	113	141				
Week	-4 to -1	0	2	4	8	12	16	20				
Visit window (days)	--	--	+/-3	+/-3	+/-3	+/-3	+/-3	+3		+ 3		
Biomarker (blood) collection: Immune protein markers		X					X		X			
Biomarker (fecal) collection: Microbiome sample**		X										
Vital signs ^j	X	X	X	X	X	X	X	X	X			
Randomization		X ^k										
Dosing ^l		X										
Dispense IMP		X	X	X	X							
IMP accountability / Collect empty wallets/cartons				X		X	X		X			
Digital photography ^m		X		X		X	X	X	X			
vIGA ⁿ	X	X	X	X	X	X	X	X	X		X	
BSA involvement (%) ⁿ	X	X	X	X	X	X	X	X	X		X	
EASI ⁿ	X	X	X	X	X	X	X	X	X		X	
SCORAD ⁿ		X	X	X	X	X	X	X	X			
POEM		X	X	X	X	X	X	X	X			
DLQI		X	X	X	X	X	X	X	X			
PP-NRS ^o	X	→							X			
SD-NRS ^p	X	→							X			
SF-12		X		X		X	X	X	X			

[figure not shown]
Procedure	Screening	Treatment Period							Week 20 Visit	Early Termination Visit ^a	ET Follow- Up Phone Call ^a	Rescue Therapy Unscheduled Visit ^b
		1	15	29	57	85	113	141				
Day	-28 to -1	1	15	29	57	85	113	141				
Week	-4 to -1	0	2	4	8	12	16	20				
Visit window (days)	--	--	+/-3	+/-3	+/-3	+/-3	+/-3	+3		+3		
HADS		X		X		X	X	X	X			
ADCT		X		X		X	X	X	X			
AE/SAE review ^d	X	→										
Concomitant medication review	X	→										
Participant diary ^f		X	X	X	X	X	X	X	X	X		
Emollient check ^g		X	X	X	X	X	X	X	X	X		

- ^a Participants who withdraw from the study early will have an Early Termination Visit and complete the assessments specified for Early Termination Visit. If due to treatment failure, this visit should be arranged within 72 hours of the start of any AD therapy, when possible. The participant will also be asked to have a final telephone call 28 days (+3 days) after taking their last dose of IMP for safety assessments. The date of this telephone call will be considered the end of study date for these participants.
- ^b Rescue Therapy Unscheduled Visit to be scheduled when rescue therapy is given outside of a scheduled visit. This visit shall be repeated each time a course of rescue therapy is considered/requested.
- ^c Informed consent (and re-consent, as applicable) must be obtained by the Principal Investigator or a licensed physician investigator (i.e., Sub-Investigator) per Good Clinical Practice (GCP) and local guidelines.
- ^d Inclusion/exclusion criteria to be assessed before first dose of IMP. Screening laboratory results will be used to confirm eligibility at Day 1 Visit.
- ^e Smoking status to include whether current-smoker, ex-smoker or never smoker, and to quantify current usage and total pack-year history.
- ^f A physical examination (PE) will be conducted at every visit. At Screening, Day 1 and Week 16 a full PE will be performed, and the following body systems will be evaluated: general appearance, cardiovascular, respiratory, gastrointestinal, musculoskeletal, central nervous system, lymph nodes and skin. At Weeks 2, 4, 8 12 and 20, a brief PE will be performed, and the following body systems will be evaluated: general appearance, cardiovascular, respiratory, gastrointestinal and skin.
- ^g BMI will be calculated from the height (collected at Screening) and weight.
- ^h Women of child-bearing potential only. Serum HCG at Screening. Pregnancy testing (urine) will be performed at the visits indicated and if a menstrual cycle is missed or if pregnancy is otherwise suspected.

- i A single ECG tracing is to be obtained on the day of the visit approximately 5 minutes after the participant has rested. If, in the opinion of the Investigator, there appear to be clinically significant findings, repeat tracings should be obtained, as necessary.
- j Blood pressure, heart rate, respiratory rate, and temperature will be measured after approximately 5 minutes after the participant has rested.
- k Participant to be randomized after all Day 1 activities are completed and patient is still eligible to participate in the study.
- l The first IMP dose will be given at the Day 1 visit after all procedures are completed following randomization. Subsequent doses are taken daily in the morning at approximately the same time ± 2 hours where possible. On study visit days, dosing may occur at home prior to the study visit, even if dosing falls outside the dosing window. Participants should refrain from consuming acidic drinks 1 hour either side of dosing and from eating 2 hours before dosing and 1 hour after dosing.
- m Digital photographs should be taken of the upper and lower body (upper & lower anterior and upper & lower posterior) as half body shots. Additional close-up photographs of up to six specific body areas (i.e., limbs, trunk and back) will also be taken. The same sites photographed at Day 1 should be followed throughout the study for each participant.
- n AD Investigator rating scales. Participants will be asked to withhold all emollients, sunscreens, or moisturizers on the day of these study visits until all study assessments are completed.
- o The Pruritus-NRS (worst itch) will be asked daily from the Screening Visit to the Week 20 Visit via a participant diary.
- p The Sleep Disturbance-NRS (SD-NRS) will be asked daily starting at the Screening Visit to the Week 20 Visit via a participant diary.
- q Adverse Events (AE) and Serious Adverse Events (SAE) will be captured from the time the participant signs the informed consent.
- r Study staff will review the patient diary with participants at each visit. Diaries will be reviewed for completeness and accuracy, and participants will be coached as needed on compliance with the protocol.
- s Patients will be asked if they have enough emollient to last them until the next study visit.
- ** A fecal sample is not required for any participant that enrolls under Protocol Version 5.0.

